## 5.3.6. Clinical Global Impression-Severity (CGI-S)

## 5.3.6.1. Definition

A secondary efficacy endpoint is the change from baseline to the end of Week 6 in the CGI-S score. The CGI-S provides an overall clinician-determined summary measure of the severity of the subject's illness that takes into account all available information, including knowledge of the subject's history, psychosocial circumstances, symptoms, behavior, and the impact of the symptoms on the subject's ability to function. The CGI-S evaluates the severity of psychopathology on a scale of 1 to 7. Considering total clinical experience with the depression population, a subject is assessed on severity of illness at the time of rating according to: 1=normal (not at all ill); 2=borderline ill; 3=mildly ill; 4=moderately ill; 5=markedly ill; 6=severely ill; 7=among the most extremely ill patients. The CGI-S permits a global evaluation of the subject's condition at a given time.

The CGI-S change from baseline at Week 6 is calculated as (CGI-S score at Week 6 – Baseline CGI-S score). Negative changes in CGI-S score indicate improvement.

#### 5.3.6.2. Analysis Methods

A frequency distribution over time of the CGI-S scores at Baseline, Day 8, Day 22, and Day 42 will be provided by treatment group. In addition, descriptive statistics of the actual values and the change from baseline will be presented by treatment group for observed case data.

The analysis of the change in CGI-S score from baseline to Day 8, 22, and 42 will be performed using an ANCOVA model on the ranks of the change in score with treatment, region, and baseline insomnia status as factors, and unranked baseline CGI-S score as a covariate.

In addition, the correlation between CGI-S score and HAM-A total score and MADRS total score will be evaluated using Spearman correlation coefficients. These correlations will look at the correlations of the actual values at each time point, as well as the change from baseline. Scatter plots will also be presented.

## 5.3.7. Sheehan Disability Scale (SDS)

#### 5.3.7.1. Definition

A secondary efficacy endpoint is the change from baseline to the end of Week 6 in the SDS. The SDS is a subject-reported, 5-item questionnaire which has been widely used and accepted for assessment of functional impairment and associated disability. The first 3 items assess disruption of (1) work/school, (2) social life, and (3) family life/home responsibilities using a 0-10 rating scale. The scores for the first 3 items are summed to create a total score of 0-30 where a higher score indicates greater impairment. It also has 1 item on days lost from school or work and 1 item on days when underproductive. The recall period for this study is 7 days.

The SDS change from baseline at Week 6 is calculated as (SDS total score at Week 6 – Baseline SDS total score). Negative changes in SDS total score indicate improvement.

## 5.3.7.2. Analysis Methods

Descriptive statistics of the actual values on Baseline, Day 8, Day 22, and Day 42 and the change from baseline to Day 8, 22, and 42 will be presented for SDS total score by treatment group. In addition, descriptive statistics of the actual values and the change from baseline, as well as a frequency distribution, will be presented by treatment group for each of the 5 SDS individual item scores at each time point.

The change from baseline to Day 8, 22, and 42 in SDS total score will be analyzed using the same MMRM as described in Section 5.2.3.1 for the primary efficacy endpoint, with the covariate "baseline MADRS total score" changed to "baseline SDS total score".

In addition, the percentage of subjects who have not worked/studied at all during the past 7 days will be summarized at each time point during the double-blind phase by treatment group.

#### 5.3.8. Patient Health Questionnaire 9-item (PHQ-9)

#### 5.3.8.1. Definition

A secondary efficacy endpoint is the change from baseline to the end of Week 6 in PHQ-9. The PHQ-9 is a 9-item, patient-reported outcome (PRO) measure to assess depressive symptoms. The scale scores each of the 9 symptom domains of the DSM-5 MDD criteria and it has been used both as a screening tool and a measure of response to treatment for depression. Each item is rated on a 4 point scale (0=not at all, 1=several days, 2=more than half the days, and 3=nearly every day). The subject's item responses are summed to provide a total score (range of 0 to 27), with higher scores indicating greater severity of depressive symptoms. The recall period is 2 weeks. The severity of the PHQ-9 is categorized as follows: None-minimal (0-4), Mild (5-9), Moderate (10-14), Moderately Severe (15-19) and Severe (20-27).

The PHQ-9 change from baseline at Week 6 is calculated as (PHQ-9 total score at Week 6 – Baseline PHQ-9 total score). Negative changes in PHQ-9 total score indicate improvement.

## 5.3.8.2. Analysis Methods

Descriptive statistics of the actual values on Baseline, Day 8, Day 22, and Day 42 and the change from baseline to Day 8, 22, and 42 will be presented for PHQ-9 total score by treatment group.

The change from baseline to Day 8, 22, and 42 in PHQ-9 total score will be analyzed using the same MMRM as described in Section 5.2.3.1 for the primary efficacy endpoint, with the covariate "baseline total MADRS score" changed to "baseline PHQ-9 total score".

As a sensitivity analysis, the change in PHQ-9 total score from baseline to the end of Week 6 will be analyzed using an ANCOVA model, using LOCF data. The derivation of the LOCF values is described in Section 5.2.3.3. The ANCOVA model will include factors for treatment, region, baseline insomnia status (present/absent), and baseline PHQ-9 total score as a continuous covariate. A 90% CI for the difference in LS Means and p-value will be calculated based on the contrast test statistic for each JNJ-42847922 dose level.

Frequency distributions of the PHQ-9 severity categories, of the 9 individual items, and of the responses to the question "How difficult have these problems made it for you to do your work, take care of things at home, or get along with other people" will be provided at each assessment time point.

In addition, the number and percentage of subjects who achieve remission of depressive symptoms (defined as a PHQ-9 total score <5) will be summarized at each time point during the double-blind phase by treatment group. Subjects who do not meet such criterion will be considered as non-remitters.

The number of subjects who are responders on depressive symptoms based on the PHQ-9 will also be evaluated. The first definition of a responder on PHQ-9 will be based on an improvement in PHQ-9 total score of  $\geq 6$  points. Based on this definition, a subject is defined a responder (yes=1) at a given time point if the improvement in PHQ-9 total score is  $\geq 6$  points.

Subjects who do not meet such criterion will be considered as non-responders and will be assigned a value of 0 (i.e., no).

The second definition of a responder on PHQ-9 will be based on a  $\geq$ 50% improvement in PHQ-9 total score from baseline. The percentage change from baseline for PHQ-9 total score is calculated as 100\*(PHQ-9 total score at Day X – Baseline PHQ-9 total score)/(Baseline PHQ-9 total score). Negative percent changes in PHQ-9 total score indicate improvement (eg, percent change < -50% indicates improvement >50%). Based on this definition, a subject is defined a responder (yes=1) at a given time point if the percent reduction in PHQ-9 total score is  $\geq$ 50%. Subjects who do not meet such criterion will be considered as non-responders and will be assigned a value of 0 (i.e., no).

For both definitions, the number and percentage of subjects who achieve a response will be summarized at each time point during the double-blind phase by treatment group. Observed case analysis, i.e., no imputation for subjects with missing values, will be explored.

The cumulative response rate, defined as the percentage of subjects experiencing at least a given value of percent reduction from baseline to the end of Week 6 in PHQ-9 total score, will be presented graphically, for both observed and LOCF data.

## 5.3.9. Snaith-Hamilton Pleasure Scale (SHAPS)

#### 5.3.9.1. Definition

A secondary efficacy endpoint is the change from baseline to the end of Week 6 in SHAPS. The SHAPS is a reliable, valid, and unidimensional instrument to assess hedonic capacity in adults with MDD. It is a 14-item, self-report tool. Each of the items has a set of 4 response categories-Definitely Agree/Strongly Agree, Agree, Disagree, and Strongly Disagree, with either of the Disagree responses receiving a score of 1 and either of the Agree responses receiving a score of 0. The subject's item responses are summed to provide a total range (range of 0 to 14). A higher total SHAPS score indicates higher levels of present state of anhedonia.

The SHAPS change from baseline at Week 6 is calculated as (SHAPS total score at Week 6 – Baseline SHAPS total score). Negative changes in SHAPS total score indicate improvement.

## 5.3.9.2. Analysis Methods

Descriptive statistics of the actual values on Baseline, Day 8, Day 22, and Day 42 and the change from baseline to Day 8, 22, and 42 will be presented for SHAPS total score by treatment group.

The change from baseline to Day 8, 22, and 42 in SHAPS total score will be analyzed using the same MMRM as described in Section 5.2.3.1 for the primary efficacy endpoint, with the covariate "baseline total MADRS score" changed to "baseline SHAPS total score".

Frequency distributions of the SHAPS individual items will be provided at each assessment time point.

# 5.3.10. Patient Reported Outcome Measurement Information System-Sleep Disturbance (PROMIS-SD)

## 5.3.10.1. Definition

The PROMIS-SD Short Form subscale consists of a static 8-item questionnaire. Using a recall period of the past 7 days, it assesses the concepts of sleep initiation (2 items), quality of sleep (3 items), early morning feelings (2 items) and worrying about sleep (1 item).

Each question has five response options ranging in value from one to five. To find the total raw score for a short form with all questions answered, sum the values of the response to each question. For the 8-item form, the lowest possible raw score is 8; the highest possible raw score is 40. Lower scores indicate less sleep disturbance. Note that the "direction" of the responses is not the same for all questions, i.e., sometimes a response of "not at all" indicates more sleep disturbance and sometimes a response of "not at all" indicates.

"My sleep quality was" ranges from 5=very poor to 1=very good

"My sleep was refreshing" ranges from 5=not at all to 1=very much

"I had a problem with my sleep" ranges from 1=not at all to 5=very much

"I had difficulty falling asleep" ranges from 1=not at all to 5=very much

"My sleep was restless" ranges from 1=not at all to 5=very much

"I tried hard to get to sleep" ranges from 1=not at all to 5=very much

"I worried about not being able to fall asleep" ranges from 1=not at all to 5=very much

"I was satisfied with my sleep" ranges from 5=not at all to 1=very much

A score can be approximated if a participant skips a question. However, for the 8-item form, at least 4 items must have been answered in order to calculate a score. After confirming that enough responses were provided, sum the response scores from the items that were answered. Multiply this sum by the total number of items in the short form. Finally, divide by the number of items that were answered. For example, if a respondent answered 5 of 8 questions and answered all items with the second lowest response option (2), you would sum all responses (10), multiply by the number of items in the short form (8) and divide by the number of items that were answered (5). Here (10x8)/5=16. If the result is a fraction, round up to the nearest whole number.

The formula is:

(Raw sum x number of items on the short form) / Number of items that were actually answered

This is a pro-rated raw score.

The raw score (i.e., the total raw score or pro-rated raw score) can be converted into a T-score for each participant based on the table in Attachment 1. The T-score rescales the raw score into a standardized score with a mean of 50 and an SD of 10.

The change in the PROMIS-SD score from baseline to each time point in the double-blind phase will be calculated, for both the raw score and the T-score.

#### 5.3.10.2. Analysis Methods

Descriptive statistics of the actual values on Baseline, Day 8, Day 22, and Day 42 and the change from baseline to Weeks 2, 4, and 6 will be presented for PROMIS-SD raw score and the T-score by treatment group.

The change from baseline to Day 8, 22, and 42 in the PROMIS-SD raw score and the T-score will be analyzed using the same MMRM as described in Section 5.2.3.1 for the primary efficacy endpoint, with the covariate "baseline MADRS total score" changed to "baseline PROMIS-SD raw score" or "baseline PROMIS-SD T-score", respectively.

Frequency distributions of the PROMIS-SD individual items will be provided at each assessment time point.

In addition, the correlations between baseline ISI score as a continuous variable and change from baseline to the end of Week 6 in the PROMIS-SD raw score and T-score will be evaluated by means of scatter plots and if appropriate, regression analysis.

# 5.3.11. Patient Reported Outcome Measurement Information System- Fatigue (PROMIS-Fatigue)

#### 5.3.11.1. Definition

The PROMIS-Fatigue Short Form subscale consists of a static 8-item questionnaire. Using a recall period of the past 7 days, it assesses a range of symptoms from mild subjective feelings of tiredness to an overwhelming, debilitating, and sustained sense of exhaustion that likely decreases one's ability to execute daily activities and function normally in family or social roles. Fatigue is divided into the experience of fatigue (frequency, duration, and intensity) and the impact of fatigue on physical, mental, and social activities. The fatigue short form is generic rather than disease-specific.

Each question has five response options ranging in value from one to five. To find the total raw score for a short form with all questions answered, sum the values of the response to each question. For the 8-item form, the lowest possible raw score is 8; the highest possible raw score is 40. Lower scores indicate less fatigue.

"I feel fatigued" ranges from 1=not at all to 5=very much

"I have trouble starting things because I am tired" ranges from 1=not at all to 5=very much

"How run-down did you feel on average" ranges from 1=not at all to 5=very much

"How fatigued were you on average" ranges from 1=not at all to 5=very much

"How much were you bothered by your fatigue on average" ranges from 1=not at all to 5=very much

"To what degree did your fatigue interfere with your physical functioning" ranges from 1=not at all to 5=very much

"How often did you have to push yourself to get things done because of your fatigue" ranges from 1=never to 5=always

"How often did you have trouble finishing things because of your fatigue" ranges from 1=never to 5=always

A score can be approximated if a participant skips a question. However, for the 8-item form, at least 4 items must have been answered in order to calculate a score. After confirming that enough responses were provided, sum the response scores from the items that were answered. Multiply this sum by the total number of items in the short form. Finally, divide by the number of items that were answered. For example, if a respondent answered 5 of 8 questions and answered all items with the second lowest response option (2), you would sum all responses (10), multiply by the number of items in the short form (8) and divide by the number of items that were answered (5). Here (10x8)/5=16. If the result is a fraction, round up to the nearest whole number.

The formula is:

(Raw sum x number of items on the short form) / Number of items that were actually answered

This is a pro-rated raw score.

The raw score (i.e., the total raw score or pro-rated raw score) can be converted into a T-score for each participant based on the table in Attachment 2. The T-score rescales the raw score into a standardized score with a mean of 50 and an SD of 10.

The change in the PROMIS-Fatigue score from baseline to each time point in the double-blind phase will be calculated, for both the raw score and the T-score.

#### 5.3.11.2. Analysis Methods

Descriptive statistics of the actual values on Baseline, Day 8, Day 22, and Day 42 and the change from baseline to Day 8, 22, and 42 will be presented for PROMIS-Fatigue raw score and the T-score by treatment group.

The change from baseline to Day 8, 22, and 42 in the PROMIS-Fatigue raw score and the T-score will be analyzed using the same MMRM as described in Section 5.2.3.1 for the primary efficacy endpoint, with the covariate "baseline MADRS total score" changed to "baseline PROMIS-Fatigue raw score" or "baseline PROMIS-Fatigue T-score", respectively.

Frequency distributions of the PROMIS-Fatigue individual items will be provided at each assessment time point.

#### 5.3.12. Patient Global Impression-Severity (PGI-S)

#### 5.3.12.1. Definition

The PGI-S is a self-report scale to measure severity of illness (1=none, 2=mild, 3=moderate, 4=severe). Considering all aspects of depression, subjects will rate their severity on the PGI-S.

#### 5.3.12.2. Analysis Methods

A frequency distribution over time of the PGI-S scores at Baseline, Day 8, Day 22, and Day 42 will be provided by treatment group. In addition, descriptive statistics of the actual values and the change from baseline will be presented by treatment group for observed case data.

The analysis of the change in PGI-S score from baseline to Day 8, 22, and 42 will be performed using an ANCOVA model on the ranks of the change in score with treatment, region, and baseline insomnia status as factors, and unranked baseline PGI-S score as a covariate.

# 5.3.13. European Quality of Life (EuroQol) Group, 5 Dimension, 5-Level questionnaire (EQ-5D-5L)

#### 5.3.13.1. Definition

The EQ-5D-5L is a standardized instrument for use as a measure of health outcome, primarily designed for self-completion by respondents. It consists of the EQ-5D-5L descriptive system and the EQ visual analogue scale (EQ-VAS). The EQ-5D-5L descriptive system comprises the following 5 dimensions: Mobility, self-care, usual activities, pain/discomfort and anxiety/depression. Each of the 5 dimensions is divided into 5 levels of perceived problems (Level 1 indicating no problem, Level 2 indicating slight problems, Level 3 indicating moderate problems, Level 4 indicating severe problems, and Level 5 indicating extreme problems).

The subject selects an answer for each of the 5 dimensions considering the response that best matches his or her health "today." The descriptive system can be represented as a health state. The EQ-VAS self-rating records the respondent's own assessment of his or her overall health status at the time of completion, on a scale of 0 (the worst health you can imagine) to 100 (the best health you can imagine.

Individual scores from the 5 dimensions will be used to obtain a weighted health status index as shown below:

- (i) Scores from each dimension will be combined to obtain a 5L profile score: eg, a score of 1 for each dimension will give a 5L profile score of 11111. Dimension scores will be combined in the following order: Mobility, Self-Care, Usual Activities, Pain/Discomfort, Anxiety/Depression
- (ii) The value set of the Health Status Index (HSI) for various values of 5L profile scores is published for Canada in the following website: https://www.ncbi.nlm.nih.gov/pubmed/26492214

(iii)The Canadian value set will be used to get the HSI values for all the countries participating in the study.

In addition, a sum score will be derived as follows: The scores of the five dimensions (values 1-5) will be added (sums between 5 and 25). From this score, subtract 5 (range 0-20) and multiply by 5 (range 0-100).

#### 5.3.13.2. Analysis Methods

Descriptive statistics of actual values on Baseline, Day 8, Day 22, and Day 42 and changes from baseline to Day 8, 22, and 42 will be provided by treatment group for the weighted EQ-5D health status index, the EQ-VAS, and the sum score.

Individual dimension responses will also be summarized at each visit with frequency counts and percentage of subjects by treatment group.

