The efficacy of study drug will be evaluated using the MADRS (SIGMA version), HAM-A (SIGH-A version), CGI-S, SDS, PHQ-9, SHAPS, PROMIS-SD (Short Form), PROMIS-Fatigue (Short Form), PGI-S, EQ-5D-5L, and WLQ (Short Form). These evaluations will be performed at the time points specified in the Time and Events Schedule. The Ruminative Response Scale (RRS) will be collected at baseline only, and will be evaluated as a potential predictor of treatment outcome.

The safety and tolerability of the study drug will be evaluated throughout the study. In addition to standard/routine assessments, the safety assessment in this study will include the ASEX, C-SSRS, and PWC.

Blood samples for PK and biomarker evaluation will be collected on the study visits specified in the Time and Events Schedule. Evening and morning salivary cortisol samples will be collected as specified in the Time and Events Schedule.

Blood samples for genetic research will be collected from subjects who consent separately to this component of the study (where local regulations permit) to allow for the identification of genetic and/or epigenetic factors that may influence the PK, efficacy, safety, or tolerability of JNJ-42847922 and to identify genetic and/or epigenetic factors associated with MDD. Subject participation in genetic research is optional. DNA samples collected from Japanese subjects will only be used for research related to JNJ-42847922 and will not be used for research related to MDD.

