Any secondary efficacy endpoint which is defined as a change from baseline will be analyzed using the same MMRM as for the primary efficacy endpoint, with the corresponding baseline as a covariate. Frequency distributions will be provided for CGI-S, PGI-S, and for the number of responders and remitters.

The correlation between baseline ISI score as a continuous variable and change from baseline to the end of Week 6 in the MADRS total score will be evaluated by means of a scatter plot and if appropriate, regression analysis. In addition, subjects will be dichotomized based on their baseline ISI score (≥15 versus <15) to evaluate whether there are differences in these subgroups (ie, evaluating change from baseline to the end of Week 6 in the MADRS total score in subjects with ISI score ≥15 versus subjects with ISI score <15). The shift in ISI score category (score 0-7=no clinically significant insomnia; score 8-14=sub-threshold insomnia; score 15-21=moderate insomnia, and score 22-28=clinically severe insomnia) from baseline to the end of Week 6 will be presented.

Subjects will also be dichotomized based on whether they have MDD with anxious distress or MDD without anxious distress to evaluate whether there are differences in these subgroups (ie, evaluating change from baseline to the end of Week 6 in the MADRS total score in subjects with and without anxious distress).

The secondary endpoint analyses will not be controlled for Type I error and nominal p-values will be presented.

The analyses for the other secondary and exploratory efficacy endpoints will be described in the SAP.

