## 5. EFFICACY

All efficacy analyses will be based on the full analysis set.

The efficacy variables for this study are listed in Table 4.

Efficacy Variable		Endpoint
MADRS	• Change from baseline to the end of Week 6 in the MADRS total score	Primary
	• Correlation between baseline ISI score as a continuous variable and change from baseline to the end of Week 6 in the MADRS total score.	Secondary
	• Change from baseline to the end of Week 6 in the MADRS total score in subjects with baseline ISI score $\geq$ 15 versus subjects with baseline ISI score	Secondary

 Table 4: Efficacy Variables

Efficacy Variable		Endpoint
	<15.	
	
 
Proportion of responders on depressive symptoms scale (≥50% improvement in the MADRS total score from baseline to the end of Week 6)
 
	Secondary
	
 
Proportion of subjects with remission on depressive symptoms scale (MADRS total score ≤8, ≤10, ≤12 at the end of Week 6)
 
	Secondary
	• Change from baseline to the end of Week 6 in the MADRS total score in subjects with MDD with anxious distress versus subjects with MDD without anxious distress.	Secondary
	• Change from baseline to the end of Week 6 in the MADRS-6 total score	Secondary
ISI	• Shift in ISI score category from baseline to the end of Week 6.	Secondary
HAM-A	• Change from baseline to the end of Week 6 in the HAM-A total score	Secondary
	
 
Proportion of responders on anxiety symptoms scale (≥50% improvement in the HAM-A total score from baseline to the end of Week 6)
 
	Secondary
CGI-S	• Change from baseline to the end of Week 6	Secondary
SDS	• Change from baseline to the end of Week 6	Secondary
PHQ-9	• Change from baseline to the end of Week 6	Secondary
SHAPS	• Change from baseline to the end of Week 6	Secondary
PROMIS-SD	• Change from baseline to the end of Week 6	Secondary
PROMIS-Fatigue	• Change from baseline to the end of Week 6	Secondary
PGI-S	• Change from baseline to the end of Week 6	Secondary
EQ-5D-5L, VAS and health status index	• Change from baseline to the end of Week 6	Secondary
WLQ	• Change from baseline to the end of Week 6	Secondary

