#### 5.3.14.2. Analysis Methods

Descriptive statistics of actual values on Baseline, Day 8, Day 22, and Day 42 and changes from baseline to Day 8, 22, and 42 will be provided by treatment group for each of the 8 items, the 4 WLQ scales, and the WLQ Productivity Loss score.

Each of the 8 items will also be summarized at each visit with frequency counts and percentage of subjects by treatment group.

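### The SAP plans no comparison with placebo for EQ-5D-5L and WLQ, although Protocol 11.3 assigns the primary MMRM to every secondary change-from-baseline efficacy endpoint

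*SAP*

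**What the plan says.** Protocol 11.3, and the synopsis in the same words, states the rule: "Any secondary efficacy endpoint which is defined as a change from baseline will be analyzed using the same MMRM as for the primary efficacy endpoint". The covariate is the corresponding baseline, there is no multiplicity control, and nominal p-values are to be shown.

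Protocol 3.1 lists EQ-5D-5L and WLQ among the efficacy measures. Protocol 2.1 places both under the patient-reported objective, which is worded as a comparison with placebo, and defines each as a change from baseline to Week 6. SAP Table 4 labels both as secondary, the EQ-5D row reading "EQ-5D-5L, VAS and health status index".

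For scales such as SHAPS the SAP follows the rule: the change "in SHAPS total score will be analyzed using the same MMRM as described in Section 5.2.3.1 for the primary efficacy endpoint". For EQ-5D-5L it does not. Descriptive statistics of values and changes "will be provided by treatment group for the weighted EQ-5D health status index, the EQ-VAS, and the sum score", and the dimension responses are tabulated by arm. For WLQ the same summaries are given "for each of the 8 items, the 4 WLQ scales, and the WLQ Productivity Loss score", plus item frequencies. No model appears in either section.

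For CGI-S the analysis of change is "performed using an ANCOVA model on the ranks of the change in score with treatment, region, and baseline insomnia status as factors", with unranked baseline as covariate. PGI-S has the same model, "and unranked baseline PGI-S score as a covariate".

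**The concern.** An endpoint to which the protocol assigned a model and a p-value has lost both in the SAP, with no note of the change. A reader of the study report could form a difference from placebo for EQ-5D-5L or WLQ only by subtracting arm means. That crude difference is not adjusted for baseline, region or insomnia status and has no planned interval. At Day 42 it also leaves out anyone without a Day 42 score, whose Day 8 and Day 22 scores an MMRM would use.

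The synopsis and Protocol 1.2 say that the results will guide the choice of doses and endpoints for Phase 3. Choosing among endpoints is easier when each has a comparable estimate of its difference from placebo. Fixing the model beforehand also removes the temptation to add one later if a by-arm table looks favourable.

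**Working it through.** No arithmetic beyond a count applies. The check sets the protocol's endpoint list against the SAP section for each scale.

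**Which endpoints count.** The count covers the secondary scale endpoints in Protocol 2.1 defined as a change from baseline. The MADRS total score subgroup and correlation endpoints are set aside because Protocol 11.3 gives them their own text. Salivary cortisol is set aside because Protocol 11.5 covers it. MADRS-6 also gets the MMRM but is not counted, because only SAP Amendment 1 introduced it.

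**What the SAP assigns.**
- Primary MMRM with own baseline: HAM-A (5.3.4.2), SDS (5.3.7.2), PHQ-9 (5.3.8.2), SHAPS (5.3.9.2), PROMIS-SD (5.3.10.2), PROMIS-Fatigue (5.3.11.2) = 6.
- ANCOVA on ranks of the change: CGI-S (5.3.6.2), PGI-S (5.3.12.2) = 2.
- By-arm descriptive statistics only: EQ-5D-5L (5.3.13.2), WLQ (5.3.14.2) = 2.
- Total: 6 + 2 + 2 = 10.

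Within the patient-reported objective the split is PHQ-9, SHAPS, PROMIS-SD and PROMIS-Fatigue (MMRM, 4), PGI-S (rank ANCOVA, 1), EQ-5D-5L and WLQ (descriptive, 2): 4 + 1 + 2 = 7 instruments.

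**Whether another passage supplies the missing analysis.**
- The last sentence of Protocol 11.3 leaves the remaining secondary and exploratory endpoints to the SAP. EQ-5D-5L and WLQ change scores are not among those remaining, because the rule has already given them a method.
- The SAP introduction says that it covers all analyses for the study report. It places only biomarker, pharmacogenomic, population PK, PD and exposure-response work elsewhere.
- SAP 5.1.1 deals with significance levels in general. Its sentence on the other endpoints is damaged in the available text. Even read alongside Protocol 11.3 (nominal 1-sided p-values), it names no model for these two scales.
- Neither SAP amendment log mentions the change.

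**Whether the data would support the model.** SAP Table 1 gives EQ-5D-5L and WLQ the same Day 8, 22 and 42 windows as HAM-A, SDS, PHQ-9, SHAPS and both PROMIS scales. The MMRM can be run on data already being collected.

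**The case against.** The strongest reply is that little is at stake. Protocol Section 11 calls itself a general description and leaves details to the SAP, the trial is not confirmatory, and secondary endpoints carry no Type I error control. All of that is true and keeps the point small. But dropping the assigned model altogether is more than a detail.

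WLQ has a better defence. A response that an item does not apply to the job is set to missing, and one unscorable scale blocks the Productivity Loss score. Fixing the subset at baseline does not cure later gaps from job changes, where missing at random is doubtful. This stands as a caveat on the WLQ estimate, but the SAP does not offer it as a reason.

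A reader might infer that CGI-S and PGI-S are equally at fault because their sections promise no scale-point difference or confidence interval. The documents do not support that. The rank ANCOVA is a planned comparison adjusted for region, insomnia status and baseline, and it suits 7-point and 4-point ordinal scales. Protocol 11.3 promises p-values for secondary endpoints, not intervals. The SDS, SHAPS and PROMIS sections, which do follow the rule, state no interval either: they cite SAP 5.2.3.1, while the 90% interval for differences is in 5.2.3.2, written for MADRS. Protocol 11.3 also mentions frequency distributions for CGI-S and PGI-S. That is no exemption from the rule, but it suggests some separate handling.

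A reader might also take the 25% dropout assumed in Protocol 11.2 as the share missing from the Day 42 tables. That does not follow. Subjects who withdraw early should have end-of-treatment assessments, and the Day 42 window opens at Day 33, so some of them will have a Day 42 value.

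**Conclusion.** The point holds for EQ-5D-5L and WLQ. The protocol assigned them the primary MMRM, and the SAP replaces it with by-arm descriptive statistics without explanation. Two of the 10 protocol endpoints under the rule, and 2 of the 7 patient-reported instruments, are therefore left with no planned comparison with placebo. For CGI-S and PGI-S the departure is one of documentation only.

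The severity is minor. The primary MCP-Mod test is unaffected and no error-controlled claim depends on these scales. The documents do not allow the effect on any estimate to be sized. The conclusion rests on reading the protocol rule as covering every secondary efficacy endpoint defined as a change from baseline, which is its plain wording.

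**What to change.** In SAP 5.3.13.2 and 5.3.14.2, apply the 5.2.3.1 MMRM with the corresponding baseline to three scores: the EQ-5D health status index, the EQ-VAS and the WLQ Productivity Loss score. Report Week 6 LS-mean differences from placebo with 90% confidence intervals and nominal p-values, using contrasts as in 5.2.3.2. The first two are the scores that SAP Table 4 names, and the third is the WLQ's single summary score. Leaving the EQ-5D sum score and the four WLQ scales descriptive is a judgement, and the SAP should say so.

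For WLQ, include only subjects with a scorable baseline Productivity Loss score, so that the subset is fixed before treatment. Report the number observed by arm and visit. State that the result covers only that subset and rests on a missing-at-random assumption that job changes may strain.

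In SAP 5.3.6.2 and 5.3.12.2, keep the rank ANCOVA and add a sentence recording the departure from Protocol 11.3 and the reason for it.

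The cost is SAP wording and three more runs of an existing model. No new data or visits are needed.
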